4.5.5 Positron Emission Tomography Scan

Two radioligands may be used in this study: florbetaben for participants at all sites (in exceptional circumstances, the use of flutemetamol may be acceptable at sites where florbetaben is not available, but only after prior written approval from the Sponsor).

Screening PET scans must not be acquired prior to the availability of potentially exclusionary screening results in order to minimize radiation burden to participants. To allow sufficient flexibility for scheduling of the screening PET scan, screening procedures (including central reading of the MRI scans) ideally should be completed within 2–3 weeks before the screening PET scan is required.

A positive PET scan using any amyloid tracer, acquired outside this study protocol is not permissible to confirm participant inclusion due to the longitudinal PET imaging requirements for all subjects enrolled in this study.

After obtaining the signed Informed Consent Form at the clinical study site, the following assessments and procedures will be performed for all participants during each amyloid PET scanning session:

- The responsible physician or his or her designee at the PET imaging center will confirm a participant's suitability for undergoing the PET imaging after a brief medical assessment, which may include weight. The PET scan should not be performed if the participant has an ongoing ARIA-E.
- For women of childbearing potential (including those who have had a tubal ligation), a urine pregnancy test will be conducted within 24 hours before the PET scan. The result must be negative for the participant to receive the amyloid tracer.
- The participant must void his or her bladder prior to scanning.
- Placement of an IV catheter into a forearm or antecubital vein for the injection of the investigational PET tracer must occur.
- A target dose of 300 [\pm 10%] MBq for florbetaben or 185 [\pm 10%] MBq for flutemetamol will be administered intravenously as a single slow bolus. The cannula

will be immediately flushed with up to 5–15 mL of saline solution. It is recognized that due to scheduling, transit, or manufacturing issues, from time to time, it is possible that an imaging center may be delivered a dose of amyloid radioligand that is less than the target dose. In these cases, participants may still be injected. However, if the dose is < 70% of the target dose, no injection should be performed and the participant should be rescheduled for imaging.

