- Additional measures for nonclinical administration by study partner (non-professional caregiver): Every 4 weeks, except when there is an in-person clinic visit, the investigator or an appointed qualified study staff will have a telephone conversation with the participant and/or study partner (non-professional caregiver) to elicit, in a non-leading way, information on medication errors and adverse events that may have occurred in the home setting. Therefore, there will be frequent contact between the study staff and the participant/study partner (non-professional caregiver). In addition, participants/study partners (non-professional caregivers) will be instructed to contact the investigator and seek approval for continued study drug dosing in the home setting in case of onset of any new symptoms or symptom worsening. These requirements will aid symptomatic ARIA-E detection and dose intervention, as described below, in the case of an asymptomatic ARIA-E that becomes symptomatic at a later date.

If BGTS ≥ 4 or symptoms develop, refer to the rule below.

- In case of occurrence of symptoms in the presence of ARIA-E (any size) or asymptomatic ARIA-E with BGTS ≥ 4 : Temporarily interrupt study drug (but continue all assessments per schedule of activities) and perform MRI monitoring at 4-week intervals until symptoms and ARIA resolve.

When symptoms and ARIA-E resolve, reintroduce study drug at the next scheduled dosing visit, at the same dose given at the time the event was detected.

Perform an MRI scan after the first dose while participants are on a Q4W dosing frequency, or after the second dose while participants are on a Q2W dosing frequency, or after the third or fourth dose while participants are on a Q1W dosing frequency.

If no new ARIA-E is detected, resume uptitration and obtain an MRI per the titration schedule. For participants on the Q1W dosing frequency, perform another MRI scan 3 months after study drug reintroduction.

- The investigator may choose to perform additional MRI monitoring for ARIA at any time.
- Symptomatic ARIA-E is defined as onset or worsening of CNS symptom(s) that is/are temporally associated with ARIA-E MRI findings.
- Any recurrence of ARIA-E: Treat using the same procedures as for the first event (based on symptoms and BGTS).

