Appendix 1: Schedule of Activities (cont.)

Table 2 Weeks 36–59 for All Participants (cont.)

Assessment/Procedure	Target Dose												UV
	Wk 36	Wk 37–39	Wk 40	Wk 41–43	Wk 44	Wk 45–47	Wk 48	Wk 49–51	Wk 52 ^a	Wk 53–55	Wk 56	Wk 57–59	
Home administration questionnaire	P&CG								P&CG				P&CG
Vital signs ^l	x								x				x
Concomitant medications	x		x		x		x		x		x		x
Adverse events ^m	x		x		x		x		x		x		x
Urine pregnancy test ⁿ									x				x
Study drug administration (dose level [mg]) ^o	S (255)	H (255)	S (255)	H (255)	H (255)	H (255)	-						
Caregiver diary ^p		x	x	x	x	x	x	x		x	x	x	

ADA=anti-drug antibody; ADAS-Cog13=Alzheimer's Disease Assessment Scale—Cognition, Subscale 13; ADCS-ADL=Alzheimer's Disease Cooperative Study Group—Activities of Daily Living; ARIA=amyloid-related imaging abnormality; ARIA-E=amyloid-related imaging abnormality-edema/effusion; ARIA-H=amyloid-related imaging abnormality-hemosiderin deposition; BL=baseline; CG=caregiver completion; C-SSRS=Columbia–Suicide Severity Rating Scale; DTI=diffusion tensor imaging; ET=early termination; H=visit appropriate for home/nonclinical administration, where applicable; I=in-clinic visit; MMA=methylmalonic acid; MMSE=Mini-Mental State Examination; MRI=magnetic resonance imaging; P=participant completion; P&CG=participant and caregiver completion; PET=positron emission tomography; PK=pharmacokinetic; Q1W=once a week; S=supervised at-clinic administration, where applicable; SLV=since last visit; T=telephone visit; UV=unscheduled visit; Wk=week.

Notes: For Q1W injections, the dosing window is ± 3 days.

Participants should return to initial planned schedule per Day 1 for subsequent visits.

For participants who terminate early, assessments listed in the ET visit should be completed.

^a Visit may be split over 2 days. All cognitive and functional assessments should be completed first. All safety assessments (e.g., vital signs, blood tests, and ECGs) should be completed on the day of dosing, prior to dosing. Whenever possible, cognitive and functional assessments and PET should be performed at the visit timepoints stipulated in the schedule of activities. However, in exceptional circumstances, if the study partner (non-professional caregiver), the primary rater, or even the participant cannot perform these assessments as per schedule of activities, they may be performed up to 4 weeks out of window.

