Appendix 1: Schedule of Activities (cont.)

Table 4 Weeks 84–104, Early Termination Visit, and Follow-Up for Participants Who Do Not Take Part in 2-Year Extension (cont.)

- ^a Visit may be split over 2 days. All cognitive and functional assessments should be completed first. All safety assessments (e.g., vital signs, blood tests, and ECGs) should be completed on the day of dosing, prior to dosing. Whenever possible, cognitive and functional assessments and PET should be performed at the visit timepoints stipulated in the schedule of activities. However, in exceptional circumstances, if the study partner (non-professional caregiver), the primary rater, or even the participant cannot perform these assessments as per schedule of activities, they may be performed up to 4 weeks out of window.
- ^b Every 4 weeks, except when there is an in-person clinic visit, the investigator or an appointed qualified study staff will have a telephone conversation with the participant and/or study partner (non-professional caregiver) to collect adverse events information and any other updates regarding the participant's health. The study staff is encouraged to have more frequent calls with a particular participant/study partner (non-professional caregiver) if considered appropriate by the investigator.
- ^c Electrocardiograph machine equipped with computer-based interval measurements. Lead placement should be as consistent as possible. The ECG recordings must be performed after the participant has been resting in a supine position for at least 5 minutes. All ECGs are to be obtained prior to other procedures scheduled at that same time (e.g., vital sign measurements, blood draws, and brain MRI scans). Circumstances that may induce changes in heart rate, including environmental distractions (e.g., television, radio, conversation), should be avoided during the pre-ECG resting period and during ECG recording.
- ^d Accurate recording of the time of study drug administration and PK sample is necessary.

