	Symptomatic ARIA-E (of any size) or asymptomatic ARIA-E and BGTS ≥ 4	
 • Temporarily interrupt study drug and perform MRI scans at 4-week intervals until symptoms and ARIA-E resolve. • When symptoms and ARIA-E resolve, reintroduce study drug at dose given at the time the event was detected. • Perform a MRI scan after the first dose while participants are on a Q4W dosing frequency, or after the second dose while participants are on a Q2W dosing frequency or after the third or fourth dose for participants on a Q1W dosing frequency. • If no new ARIA-E is detected, resume uptitration and obtain an MRI per the titration schedule. For participants on the Q1W dosing frequency, perform another MRI scan 3 months after study drug reintroduction.
	Any recurrence of ARIA-E	
 • Treat the same as the first event (based on symptoms and BGTS).
ARIA-H	ARIA-H > 15 cumulatively (should not include any disseminated LH)	
 • Permanently discontinue study drug.

ARIA-E = amyloid-related imaging abnormality—edema/effusion; ARIA-H = amyloid-related imaging abnormality— hemosiderin deposition; BGTS = Barkhof grand total score; LH = leptomeningeal hemosiderosis; MRI = magnetic resonance imaging; Q1W = once a week; Q2W = every 2 weeks; Q4W = every 4 weeks.

The investigator may choose to perform additional magnetic resonance imaging (MRI) monitoring for amyloid-related imaging abnormality (ARIA) at any time.

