5.1.1 Visit Windowing

The analysis of data will be undertaken using reporting windows. As all the endpoints in the study are collected at different time frequencies, different sets of reporting windows will be applied depending on the frequency of assessments. In case of more than one assessment within a time window, the assessment with the date closest to the target (scheduled) day will be selected.

For amyloid PET assessments, time windows will be used ([Table 2](#)). Because of visit windowing, data collected at an early termination visit will be summarized at the appropriate time in the trial. For participants who have discontinued treatment early, if a PET scan is performed more than 56 days after the date of last dose, the PET scan will not be used for the analysis.

Table 2 Time Windows for Amyloid PET Endpoints

Visit	Target study day	Time window
Baseline	1	Up to day 1
Week 52	365	281, 449
Week 104	729	645, 813

For endpoints of home administration questionnaire (Caregiver or Patient), time windows will be applied ([Table 3](#)).

Table 3 Time Windows for Home Administration Questionnaire Endpoints

Visit	Target study day	Time window
Baseline	- (no baseline assessment planned)	- (no baseline assessment planned)
Week 36	253	2, 308
Week 52	365	309, 448
Week 76	533	449, 630
Week 104	729	631, 770

For cognitive and functional endpoints, time windows will be applied ([Table 4](#))

Table 4 Time Windows for Cognitive and Functional Endpoints

Visit	Target study day	Time window
Baseline	1	Up to Day 1
Week 24	169	2, 266
Week 52	365	267, 448
Week 76	533	449, 630
Week 104	729	631, 770

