5.3.3 Main Analytical Approach for Primary Endpoint

Descriptive summary statistics for the brain amyloid CL load at baseline, Week 52 and Week 104 as well as the change from baseline to Week 52 and to Week 104 will be produced on both the ITT and Amyloid-PET-longitudinal analysis sets. Descriptive summaries of the primary endpoint will present the mean, standard deviation, median, and minimum and maximum.

A Mixed Model for Repeated Measures (MMRM) analysis will be used to estimate the mean change in CL from baseline to Week 52 and to Week 104 on the ITT analysis set. The model will include the change from baseline in CL as the dependent variable, while adjusting for visit (as categorical), apolipoprotein E allele $\epsilon 4$ (APOE $\epsilon 4$) status (as categorical; carrier vs non-carrier), baseline CL, and baseline CL-by-visit. Visit will be treated as the repeated variable within a participant. An unstructured variance-covariance matrix will be applied to model the within-participant errors; in the case of non-convergence, compound symmetry will be used, together with a robust estimator of standard error ("sandwich" estimator).

In line with the primary estimand definition, data acquired after the ICE "Substantial reduction in drug exposure due to the COVID-19 pandemic" (as defined above) or more than 56 days from date of last dose will be excluded from the analysis and treated as missing for the primary analysis purposes.

There will be no data imputation for missing data. However, the MMRM model provides unbiased estimates and valid inference in the presence of missing data, under the MAR (missing at random) assumption.

The least squares means at Week 52 and at Week 104 will be estimated and presented with a 95% CI.

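### PET scans deferred for ARIA-E: two protocol rules and the 4-week lateness allowance do not fit the SAP window, and the SAP words its 56-day exclusion in two ways

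*Protocol*

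**What the plan says.** **Hold rule.** For symptomatic ARIA-E of any size, or asymptomatic ARIA-E with BGTS of 4 or more, Protocol 5.1.3.1 says: "Temporarily interrupt study drug (but continue all assessments per schedule of activities) and perform MRI monitoring at 4-week intervals until symptoms and ARIA resolve". The schedule of activities includes PET at Weeks 52 and 104. Appendix 2 restates the rule without the clause on assessments: "Temporarily interrupt study drug and perform MRI scans at 4-week intervals until symptoms and ARIA-E resolve".

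**PET bar.** Protocol 4.5.5: "The PET scan should not be performed if the participant has an ongoing ARIA-E". It has no BGTS or symptom threshold. It therefore also covers asymptomatic ARIA-E with BGTS 1 to 3, where 5.1.3.1 continues dosing.

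**Lateness allowance.** Footnote a to Appendix 1 Tables 2, 4 and 5 says: "Whenever possible, cognitive and functional assessments and PET should be performed at the visit timepoints stipulated in the schedule of activities". In exceptional circumstances, when the partner, rater or participant cannot do the assessments, "they may be performed up to 4 weeks out of window". ARIA-E is not named.

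**What the SAP accepts.** SAP Table 2 takes PET on Days 281 to 449 for Week 52 and Days 645 to 813 for Week 104. SAP 5.1.1 adds an exclusion: "For participants who have discontinued treatment early, if a PET scan is performed more than 56 days after the date of last dose", the scan is not used. SAP 5.3.3 states the exclusion for the primary MMRM without the opening qualifier: data "more than 56 days from date of last dose will be excluded from the analysis and treated as missing". SAP 5.3.2 lists two intercurrent events, COVID-19-related loss of exposure and treatment discontinuation. A temporary ARIA-E hold is neither.

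**The concern.** A site with a participant on an ARIA-E hold at Week 52 or 104 reads one section that continues everything and another that bars the PET. If the PET is deferred, the only written allowance is 4 weeks, for reasons that do not include ARIA-E. Nothing says what to do after that, although the SAP would still use the scan.

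Missing scans would then follow ARIA-E. The protocol describes ARIA-E as dependent on dose and APOE ε4, and its management changes exposure. The primary MMRM assumes missing at random and adjusts for visit, ε4 carriage, baseline CL and baseline-by-visit, but not for ARIA-E or exposure. The sensitivity analyses in SAP 5.3.4 vary only the COVID-19 rule, and the completers analysis in 5.3.5 does not address selective loss.

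The two wordings of the 56-day rule matter separately, because they decide which acquired scans enter the primary analysis.

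**Working it through.** **1. The SAP window (Table 2).** Target day = 7 × week + 1.
- Week 52: 7 × 52 + 1 = 365; 449 − 365 = 365 − 281 = 84 days.
- Week 104: 7 × 104 + 1 = 729; 813 − 729 = 729 − 645 = 84 days.

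The SAP's figures reproduce as target ± 12 weeks.

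**2. The protocol limit.** Target + 28 days, or + 31 if the ± 3-day Q1W window is added first.
- Week 52: Day 393 or 396, against 449.
- Week 104: Day 757 or 760, against 813.
- Gap at each visit: 56 or 53 days.

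**3. Routine MRI rechecks that fit.** Assume ARIA-E is found on an MRI 7 to 13 days before the Week 104 visit (the spacing in the Appendix 1 MRI footnote), so on Days 716 to 722. Four-weekly rechecks fall on Days 744–750, 772–778, 800–806 and 828–834. One falls inside the protocol limit and three inside the SAP window.

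**4. The 56-day rule.**
- *Unresumed hold, scan on time.* 729 − 56 = 673. Take a participant who is not in the extension, is on a temporary hold, was last dosed before Day 673 and is scanned on Day 729. SAP 5.1.1 keeps the scan; 5.3.3 read literally drops it.
- *Deferred scan after a Week 103 dose.* Week 103 is Day 7 × 103 + 1 = 722, and 722 + 56 = 778. If this is the final dose, 5.1.1 allows use to Day 813, while 5.3.3 stops at Day 778, which is 35 days earlier.
- *Hold starting at the pre-visit MRI, no later dose.* With the last dose up to 6 days before the MRI (Days 710 to 722), 5.3.3 stops at Days 766 to 778. That is 6 to 21 days beyond the protocol limit (766 − 760; 778 − 757). If the last dose was on or before Day 701 (757 − 56) or 704 (760 − 56), nothing is gained.

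**5. Precision.** 95% half-width = 1.96 × 25.67 / √n, with the SD from SAP Section 3. Reading the 10 CL interval as total width gives (1.96 × 25.67 / 5)² = 101.3, so 102 evaluable. Against the 150 that the SAP calls required, this implies 1 − 102/150 = 32% loss, near the stated figure of around 35% (102/0.65 would be 157). With 192 enrolled and 35% loss, n = 124.8. The documents do not give the share with ongoing ARIA-E at a PET visit, so the further loss is an assumed range:

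| Further loss, % of 192 | Scans | n | Half-width (CL) |
|---|---|---|---|
| 0 | 0 | 124.8 | 4.50 |
| 1 | 1.9 | 122.9 | 4.54 |
| 2 | 3.8 | 121.0 | 4.57 |
| 5 | 9.6 | 115.2 | 4.69 |
| 10 | 19.2 | 105.6 | 4.90 |

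All stay under 5 CL.

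**The case against.** **General rule and specific exception.** The hold rule can be read as general and the PET bar as its exception, checked by the imaging-centre physician at each session. That reading is reasonable, and the PET Technical Operations Manual, not available here, may say so. It reduces the conflict to a missing cross-reference, but does not settle how late a barred PET may be taken.

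**Nothing is discarded by the 4-week limit.** A reader might infer that the protocol limit removes scans from the analysis. It does not. It governs when sites scan, and SAP Section 1 gives the SAP precedence. A scan taken on, say, Day 800 would be analysed, subject to the 56-day rule. The possible loss is of scans never taken.

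**Week 56 is not a last chance.** A reader might infer that 4-weekly MRI leaves a single recheck before the limit. Both 5.1.3.1 and Appendix 2 let the investigator add MRIs at any time, so step 3 counts only routine ones.

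**The 56-day mismatch is narrow.** SAP 5.3.3 introduces the exclusion as following from the estimand, which points to treatment discontinuation. Once dosing resumes, the last dose is recent, so a scan after a completed hold is safe. What remains is the unresumed hold and the late Week 104 scan in step 4.

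**Radiation.** At 5.8 + 0.1 = 5.9 mSv per scan (Protocol 5.1.2.1), two scans give 11.8 mSv, above the 10 mSv annual EU figure cited there. A Week 52 scan on Day 449 is 280 days before Day 729. This stands as a cost, although the existing allowance already permits 336 days (729 − 393). The early-termination PET footnote supplies a suitable condition.

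**Conclusion.** The point holds as a coordination gap. The hold rule and the PET bar must be reconciled, the protocol allowance is 53 to 56 days shorter than the SAP window, and the 56-day exclusion has two scopes. No hypothesis is tested, and the effect on precision is minor over the assumed range. What remains is missingness linked to ARIA-E that no planned analysis examines.

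A reader might try to turn the predicted ARIA-E rate of about 26% (0.26 × 192 ≈ 50 participants) into a count of lost scans. The documents do not support that. The rate is predicted for the pivotal schedule over the whole of treatment, no ARIA-E durations are given, and Protocol 5.1.1.1 says that onset tends to be early. Many events would also be asymptomatic with low BGTS, outside the hold rule, although still under the PET bar.

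Timing limits the benefit. SAP 5.8.1 expects about 180 of 192 participants to have had the opportunity to complete Week 52 by 30 June 2022, so a footnote change mainly helps Week 104, where early onset suggests fewer cases. The full gain to Day 813 also needs dosing to continue or resume, or the 56-day rule aligned to 5.1.1.

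**What to change.** 1. Reconcile Protocol 5.1.3.1, 4.5.5 and Appendix 2 on whether PET is among the assessments that continue during ongoing ARIA-E, and cross-reference them. The choice belongs to the sponsor.
2. If PET is to be deferred for ARIA-E, say in the footnotes to Appendix 1 Tables 2, 4 and 5 that it may be acquired up to the SAP window edge (Day 449 or Day 813). Make this subject to the condition already in Table 4 footnote m: at least 6 months since the previous amyloid PET and within the local annual radiation limit. The effect on the next scheduled PET should be checked too.
3. Make SAP 5.3.3 match 5.1.1 and the estimand, so that the 56-day exclusion applies only after permanent early treatment discontinuation.

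The cost is a protocol clarification and one SAP qualifier, with no scans beyond those scheduled. The small downside is a few later scans, inside the spread the SAP already accepts, and closer spacing to the next PET.

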4.5.6 Home Administration Assessments

The assessments described in this section will be performed as outlined in the schedule of activities (see [Appendix 1](#)) and in the order specified in Section [4.6](#).

Whenever possible, there should be consistency in the rater and study partner (non-professional caregiver) who complete the scales for each participant throughout the duration of the study. Potential raters will receive training and be approved by the rating scale contract research organization (CRO) prior to being allowed to administer any cognitive assessments or rating scales in the study.

Whenever possible, cognitive and functional assessments should be performed at the visit timepoints indicated in the schedule of activities (see [Appendix 1](#)). However, in exceptional circumstances for post-Day 1 visits, if the study partner (non-professional caregiver), the primary rater, or even the participant cannot perform these assessments as per the schedule of activities, they may be performed up to 4 weeks out of window.

Given that cognitive and functional assessments used for eligibility and as exploratory outcome measures in this trial involve subjective judgment, the adequacy of participant and study partner (non-professional caregiver) interviews and ratings will be monitored by an endpoint reliability program administered by the rating scale vendor; this is considered an essential part of good research methodology. For some eligibility assessments as well as for some other scales, audio recordings may be used for quality assurance purposes. Prior studies have clearly demonstrated that the failure to adequately monitor such ratings can substantially increase the risks of failed trials (Becker and Greig 2008; Kobak 2010).

